medical or surgical intensivist physicians. Our co-investigator, Drs. [name], is chief of the medical critical care service. [name] is the Director of the Center for Nursing Research, and [name] holds an appointment as a nurse scientist, in addition to her faculty role. The APH Pediatric Specialty Diagnostic Laboratory is part of Orlando Health, and will run the α -amylase assays. [name] (co-investigator) provides leadership for the laboratory, and is an expert in biomarkers of microaspiration. Drs. [name] and [name] are faculty members at UCF and will be involved in data management and analysis. Team members have worked together on many previous studies, including our R21.

Sample. Subjects (n=560) will be enrolled if they meet the following **inclusion criteria**: 1) 18 years of age or older; 2) orally intubated with ETT and treated with MV; 3) 24 hours or less since intubation; and 4) expected to be intubated for at least 36 hours after enrollment. **Exclusion criteria** are: 1) documented aspiration at time of intubation; 2) *intubation to treat known aspiration*; 3) treatment with rescue MV therapies (high-frequency oscillator ventilation or extracorporeal membrane oxygenation); 4) re-intubation for any reason; 5) contraindications to receiving the intervention (e.g., oral injuries); 6) history of lung or head/neck cancers that may produce α -amylase in the lungs; 7) history of disease that affects saliva production (e.g., Sjögren's syndrome); and 8) prisoners. Eligible subjects are available. In fiscal year 2012, 1,641 patients were treated with MV on the study units (median=4 days; mean=6.2 days). On average, 28 patients are ventilated each day. Patients on MV are split between the medical and surgical intensivist teams, providing a diversity of diagnoses. We will have a large pool of patients who are highest risk: trauma, burn, and neurological conditions.⁴⁸

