Randomization. Our biostatistician will oversee the process of randomization of subjects to either the NO-ASPIRATE or usual care group. He will develop a blocked randomization procedure, using different sized blocks, to ensure balanced assignment without being able to predict group assignment.¹⁶⁶ Because many subjects will be intubated with the specialized SS-ETT (about 65% from historical data), we will stratify randomization by type of ETT to ensure that approximately half of those with and without the SS-ETT are randomly assigned to each group. Stratification will help to address type of tube as a potential confounding variable, and will allow for secondary sub-group analysis. A member of the study team not involved in data collection will place group assignments for each type of ETT in numbered, sealed, opaque envelopes. Upon enrollment, study personnel will identify the type of ETT, and open the appropriate envelope to determine group assignment. Only study team members who provide the intervention will know the subjects' assigned groups. ICU personnel, as well as subjects and family members, will be blinded to the assignment.

Intervention. Following enrollment, the RA will collect baseline data, implement the assigned intervention (NO-ASPIRATE or usual care/sham), and collect specimens. The RA will then implement the intervention as designated by study arm every 4 hours. *Figure 4 summarizes the procedures for each group.*

To control for possible differences in usual oral care practices, the RA will perform oral cleansing and suctioning with a suction swab after delivering the NO-ASPIRATE or sham intervention using the hygiene components from the oral care kit. The RA will also perform tooth brushing every 12 hours. Oral antisepsis will be done after obtaining specimens for α -amylase. Some subjects may require additional oral suctioning for secretion management; staff will use the available tonsil suction device for oral suctioning in-between the scheduled interventions and document in the medical record. Additional necessary oral suctioning will be recorded and controlled for, if applicable.

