Endpoints. The intervention will be delivered per protocol until one of the following endpoints is met (whichever occurs first): 1) ETT removed (extubation); 2) tracheostomy performed; 3) 14 days of enrollment; or 4) other exclusion criterion met (e.g., rescue ventilation). *Extending the intervention to 14 days will allow us a better opportunity to address the secondary aim of VAC. At the study site, the median time to tracheostomy is 8 days; 85% of patients on prolonged MV undergo a tracheostomy by Day 14.*¹¹² *This duration of enrollment is longer than that reported in other intervention studies,*^{19,73,109} *and will allow us to test the effect of the intervention on both microaspiration and VAC prevention for an extended period. Subjects must be enrolled at least 36 hours to be included in analysis. Since the duration of MV varies and we want to assess the effect of our intervention on preventing microaspiration, we determined (with input from consultants) that a minimum enrollment of 36 hours would provide adequate samples to address the primary aim.*

Measurement of Primary and Secondary Outcome Variables

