VAC. VAC will be determined using the CDC/NHSN criteria (Figure 6, blue boxes).¹⁶ We will assess ventilator data (FiO₂ and PEEP) daily from the medical record to assess for worsening oxygenation status. Per consultation with [name], we will assess for VAC for 2 days beyond the last intervention. To address Aim 2 and hypotheses 2.1 and 2.2, we will record VAC as positive or negative. We will also record the time to VAC in days (0.1 day increments). Determination of VAC will be made by our intensivist co-investigator. The CDC/NHSN algorithm proceeds to determine if VAC is infection-related (grey part of algorithm).¹⁶ *Our primary endpoint is VAC as a broad complication that includes both infectious and noninfectious etiologies; however, we will also report possible and probable VAP in our analyses as applicable.*

Tracheal/Oral Ratio of α -Amylase. To address Aim 3 and hypothesis 3.1, the ratio of the tracheal value to the oral value of α -amylase for each paired sample will be calculated.

Training and Data Management

Personnel Training and Fidelity. The PI will be responsible for training and will be assisted by the PD in ensuring that all personnel are knowledgeable in their roles. At the beginning of the study, the PI and PD will develop a comprehensive study Operations Manual, which will include procedures and checklists for subject enrollment, delivery of the NO-ASPIRATE and usual care/sham interventions, data collection, and ongoing

reporting related to the study (e.g., IRB and DSMB). All study personnel will complete the required CITI training on protection of human subjects and will sign confidentiality agreements.

The PI and PD will train the RAs in all study-related procedures. Initial training for the NO-ASPIRATE intervention, the usual care/sham intervention, and specimen collection will be conducted in a simulation laboratory, followed by observation in the clinical setting. Inter-rater reliability will be established for delivery of the NO-ASPIRATE and usual care/sham interventions, and for review of the medical record for study-related data. A kappa of at least .90 will be achieved between data collectors. To ensure treatment fidelity, additional re-assessment and related training will be done every 6 months using a standard observation checklist.

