Subjects will be randomly assigned to each of the two treatment groups at 1:1 ratio. Before analysis, data will be carefully examined for accuracy. Every effort will be made to avoid missing data. Subject characteristics at baseline will be examined to ensure a sound balance on demographic variables between the two groups. For continuous demographic variables, independent two-sample *t* tests will be used to detect differences between the two groups. For categorical demographic variables, the Pearson's chi-square test will be used to examine differences between the two groups. If subject subsets are found to be significantly different for a demographic variable, then this variable will be included into the statistical models. All planned analyses will be based on the intent-to-treat (ITT) population, which consists of all subjects who have been randomized into the NO-ASPIRATE or usual care group. In all analyses, an alpha level of 0.05 will be used.

[figure not shown]

Figure 6. Algorithm for Determining VAC

Aim 1. To compare the effects of the NO-ASPIRATE intervention versus usual care on microaspiration of gastric and oral contents in critically-ill intubated patients. Hypothesis 1.1.

Subjects in the NO-ASPIRATE group will have a significantly lower percentage of tracheal secretions with α -amylase present as compared to those in the usual care group. **Analysis 1.1.** Percentages of tracheal secretions α -amylase present for both groups will be computed. The percentage difference between the two groups will be calculated along with the 95% confidence interval for the percentage difference. The logistic regression including covariates of interest will be used to assess the percentage difference adjusting for the prognostic covariates.

Hypothesis 1.2. Subjects in the NO-ASPIRATE group will have a lower mean value of α -amylase in tracheal secretions as compared to those in the usual care group. **Analysis 1.2.** Values of α -amylase in tracheal secretions will be collected for each subject every 12 hours during study. Treatment effect based on these values over time will be evaluated by the generalized linear models using the generalized estimating equation (GEE) method.^{124,125} In addition, the generalized linear models with prognostic covariates of interest will be used to assess change in mean values of α -amylase over time adjusting for prognostic covariates.

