We will include children ages 18-20 who meet eligibility criteria. Approximately 9% of the population is in this age range. In particular, younger patients are admitted to the surgical/trauma critical care service line. Patients with burn, trauma, and neurological injury are at highest risk for infection, and are often younger. Therefore, it is important to include this age group.

We will include the elderly as they are at an increased risk for complications of MV secondary to chronic illness and decreased immune response, and their mortality for VAC (lung injury) is higher than younger patients.¹²⁸ We will also include pregnant women because if they require MV, oral care interventions are not any different for them, and the NO-ASPIRATE intervention is enhanced oral care.

Although children less than 18 years of age are sometimes treated in the adult ICUs, we will exclude them because the VAC criteria specifically note applicability only to those 18 years of age and older.¹⁶

We will exclude prisoners.

Describe procedures for assignment to a study group. As related to human subjects' protection, describe and justify the selection of an intervention's dose, frequency, and administration.

Our biostatistician will oversee the process of randomization of subjects to either the NO-ASPIRATE or usual care group. He will develop a blocked randomization procedure, using different sized blocks, to ensure balanced assignment without being able to predict group assignment.¹⁶⁶ Because many subjects (about 65% to 70% from historical data) will be intubated with the specialized subglottic suction ETT (SS-ETT), we will stratify randomization by traditional or SS-ETT to ensure that approximately half of those with and without the SS-ETT will be randomly assigned to each group. This will help to address type of tube as a potential confounding variable, and will allow for secondary sub-group analysis. A member of the study team, who will not be involved in data collection, will place group assignments in sequentially-numbered, sealed, opaque envelopes for each type of ETT. Upon enrollment, study personnel will identify the type of ETT inserted, and open the appropriate envelope to determine group assignment. Only study team members who provide the intervention will know the subjects' assigned groups. Hospital staff members, as well as subjects and their family members, will be blinded to group assignment.

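### The 36-hour minimum for inclusion in analysis contradicts the plan's intent-to-treat population, and nothing says which rule prevails

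*Combined protocol and SAP*

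**What the plan says.** Two statements in the combined protocol and SAP define who is analysed.

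- Endpoints: "Subjects must be enrolled at least 36 hours to be included in analysis". The reason given is that "a minimum enrollment of 36 hours would provide adequate samples to address the primary aim". The rule is not limited to one aim or to a secondary analysis.
- Data Analysis: "All planned analyses will be based on the intent-to-treat (ITT) population, which consists of all subjects who have been randomized" to either group. No 36-hour condition appears there.

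Four other places bear on whether the two can be reconciled.

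- Randomization: "Upon enrollment, study personnel will identify the type of ETT, and open the appropriate envelope to determine group assignment". Human Subjects, section A, repeats this almost word for word.
- Sample, and again Human Subjects, section A: the entry criterion is that the patient is "expected to be intubated for at least 36 hours after enrollment".
- Power Analysis and Human Subjects, section A: 560 are enrolled for a final sample of 400. The Power Analysis calls the difference attrition. Human Subjects describes the final 400 as randomised subjects.
- VAC measurement: ventilator data come daily from the medical record, and "we will assess for VAC for 2 days beyond the last intervention".

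**The concern.** An exclusion applied after assignment gives up part of what randomisation protects. Endpoints lists extubation and rescue ventilation among the events that end the intervention. Either could happen before 36 hours, and either may be related to outcome. Rescue ventilation is of particular interest, because VAC is itself defined by worsening oxygenation. If leaving early is related to both arm and outcome, the comparison among those who stay is biased.

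The contradiction also leaves the primary analysis set open for every hypothesis. As written, the set could be settled after data are seen, and a 36-hour set could be reported under the intent-to-treat label.

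**Working it through.** **1. Can both rules hold?** Take a subject randomised at hour 0 who is extubated at hour 20. Data Analysis includes this subject and Endpoints excludes them. There are three possible ways out:

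- *Randomisation delayed to 36 hours.* No: the envelope is opened at enrollment (Randomization; Human Subjects, section A).
- *Entry criterion removes such subjects.* No: it concerns expected duration, and Endpoints itself gives variable ventilation time as grounds for a minimum.
- *A second population is defined.* No: there is no modified intent-to-treat, per-protocol or sensitivity set.

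**2. Does the sample size settle it?** 400 × 1.40 = 560 reproduces the enrollment target. The allowance is 160/560 = 28.6% of those enrolled. A final 400 fits a reduced analysis set, but the loss is attributed to attrition of unspecified kind, and neither place mentions the 36-hour rule or ranks it against intent-to-treat.

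**3. Does the reason cover every aim?** It concerns specimens, so it can apply to the α-amylase hypotheses (H1.1, H1.2, H3.1). It cannot apply to VAC (H2.1, H2.2), which needs no specimen.

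**4. How many are affected?** Not stated. Sample gives site ventilation times of median 4 days and mean 6.2 days, before the 36-hour expectation is applied. Entry is within 24 hours of intubation, so an early leaver has at most 24 + 36 = 60 hours (2.5 days) of intubation, below that unscreened median. This does not fix the share.

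**5. Power illustration, H1.1.** Assumptions: control rate 46% and intervention rate 31% (the two pilot samples, 13 subjects); 15% read as percentage points; one binary result per subject, with a specimen from each; two-sided .05; n per arm. With Δ = p₁ − p₂ and p̄ their mean:

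Power = Φ{[Δ√n − 1.96 √(2p̄(1−p̄))] / √(p₁(1−p₁) + p₂(1−p₂))}

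- 400 analysed (n = 200): (2.121 − 1.349)/0.680 = 1.136, power **0.872**. The plan states .87.
- 560 analysed (n = 280), full effect in everyone: (2.510 − 1.349)/0.680 = 1.708, power **0.956**.
- 560, with 10% short-stay and no effect in them: Δ = 0.15 × 0.90 = 0.135; (2.259 − 1.354)/0.684 = 1.324, power **0.907**.
- 560, with 28.6% short-stay and no effect in them: Δ = 0.15 × 400/560 = 0.107; (1.793 − 1.361)/0.690 = 0.625, power **0.734**.

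The choice of set can therefore move power to either side of the stated .87. These figures describe dilution under intent-to-treat. They do not measure bias from the exclusion.

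**The case against.** The best defence is that the planners' intention can be read from the numbers: they sized the trial on a reduced set of 400, in line with the 36-hour rule, and the entry criterion should keep early leavers few. The rule also falls equally on both arms. ICU staff, subjects, families and laboratory personnel are blinded, so extubation and rescue decisions should not depend on the assignment.

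Much of this stands. The entry criterion and the site durations argue against a very large group, and symmetry and blinding limit bias. They do not exclude it: equal wording does not ensure equal selection if treatment affects who leaves early, and Solutions to Potential Issues concedes that assignment may become known. Nor does a final sample of 400 override an explicit statement that all analyses use all randomised subjects.

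A reader might infer that the rule would remove 160 of 560 subjects, or that following intent-to-treat would cut power to 0.73. The documents support neither. The 160 covers attrition from all causes, and 0.734 also needs no effect at all in every short-stay subject. With 10% short-stay, power is still above the stated .87. A reader might also infer that the result will be biased in a known direction, or that a choice after seeing data is intended. Nothing in the documents shows either. The point is that the plan leaves room for it.

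**Conclusion.** The contradiction is real and needs to be resolved before unblinded data are seen. It rests on the text alone: two unqualified rules, assignment at enrollment, an entry criterion about expectation only, and no statement of precedence. It reaches the primary aim and, without any supporting reason, VAC.

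Its numerical size is unknown. The number under 36 hours is not given, and the size and direction of any bias cannot be derived from the documents. The H1.1 range of 0.734 to 0.956 on 560 depends on the pilot rates, a simplified one-result-per-subject test, and assumed short-stay shares of 0% to 28.6%. It shows only that the choice of set matters.

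**What to change.** - **Endpoints:** remove the 36-hour condition as the rule for the primary analysis. Keep it as a labelled sensitivity analysis.
- **Data Analysis:** name one primary set per aim. For VAC (H2.1, H2.2): all randomised subjects by assigned group. For α-amylase (H1.1, H1.2, H3.1): all randomised subjects by assigned group, with no minimum duration. Those without a specimen (a pair for H3.1) cannot contribute, and should be reported by arm with reasons, using the record of omissions already planned under specimen collection. A named modified intent-to-treat set is one way to word this.
- **Data Analysis, early leavers:** state whether the enrollment specimen alone qualifies a subject for the α-amylase set, that a specimen not taken is missing and not negative, and how VAC status is recorded for those who leave early.
- **Power Analysis and Human Subjects, section A:** state which population the 400 and each power figure describe, and reconcile the description of the 400 as randomised with 560 randomised at enrollment.

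No new data are needed, but the attrition allowance must be re-explained if all randomised subjects are analysed for VAC. Short-exposure subjects may dilute the effect. Before 36 hours at most three specimens are scheduled (enrollment, 12 and 24 hours), so per-subject percentages are imprecise; with one specimen only 0% or 100% is possible. Tracheal specimens are taken only when suctioning is indicated, so the α-amylase set remains partly selected after randomisation. That should be acknowledged in the plan.
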